7.2.2.1 Safety of Imetelstat as Monotherapy in Hematologic Malignancies

Cytopenias, particularly thrombocytopenia and neutropenia, are the primary dose limiting toxicities (DLTs) identified with imetelstat. The frequency and severity of all cytopenias, particularly thrombocytopenia and neutropenia, are associated with the imetelstat dose intensity (actual dose and frequency of dosing); however, cytopenias are manageable through dose modifications, reversible and of short duration, and with limited clinical consequences, for example febrile neutropenia.

Completed Monotherapy Studies in Hematologic Diseases

[REDACTED]

Ongoing Study 63935937/MDS3001 (NCT02598661) in Low- or Intermediate-1 Risk MDS

Treatment with imetelstat was generally well tolerated and consistent with the existing safety profile. The most common TEAEs (cytopenias) were predictable and manageable, and for the majority of events in Part 1 these were reversible.

[REDACTED]

For complete safety information on imetelstat please refer to current Investigator's Brochure provided in the context of this protocol.

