9.3.2 Events not to be treated as SAEs

Due to the seriousness of the disease in this study, certain conditions defined as SAEs will be excluded from expedited reporting on a SAE report form.

- Elective hospitalization and surgery for treatment of the underlying disease including transfusions
- Elective hospitalization to simplify treatment or study procedures

- Events that are only and unequivocally caused by progression of the underlying disease, except transformation to AML which is always to be reported as an SAE

Primary disease progression and related SAEs, e.g., hospitalization for surgery/diagnostic procedures, except for life-threatening status or death caused by the underlying malignant disease will not be considered and reported as SAEs if they are unrelated to study medication according to the investigator. The assessment of relationship to study medication must also be documented.

Further information on safety reporting can be found in the study specific Safety Management Plan.

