Progressive disease (PD)	Evidence for an increase in bone marrow blast percentage and/or increase of absolute blast counts in the blood: 
 >50% increase in marrow blasts over baseline (a minimum 15%-point increase is required in cases with <30% blasts at baseline; or persistent marrow blast percentage of >70% over at least 3 mo; without at least a 100% improvement in ANC to an absolute level ($>0.5 \times 10^9/L$ [500/μL], and/or platelet count to $>50 \times 10^9/L$ [50 000/μL] non-transfused); or >50% increase in peripheral blasts (WBC x % blasts) to $>25 \times 10^9/L$ (>25 000/μL) (in the absence of differentiation syndrome)†; or New extramedullary disease
Hematologic relapse (after CR, CR _i)	Bone marrow blasts $\geq 5\%$; or reappearance of blasts in the blood; or development of extramedullary disease
Hematologic improvement (HI)	
Erythroid response (HI-E)	
NTD (0 RBCs in 16 wk)*	At least 2 consecutive Hb measurements ≥ 1.5 g/dL for a period of minimum 8 wk in an observation period of 16 to 24 wk compared with the lowest mean of 2 Hb measurements (apart from any transfusion) within 16 wk before treatment onset‡; only a response duration of at least 16 wk, however, is considered clinically meaningful
LTB (3-7 RBCs in 16 wk in at least 2 transfusion episodes, maximum 3 in 8 wk)*	Transfusion independence, defined by the absence of any transfusions for at least 8 wk in an observation period of 16-24 wk with the same transfusion policy (defined below) compared with 16 wk prior to treatment; only a response duration of at least 16 wk, however, is considered clinically meaningful
HTB (≥ 8 RBCs in 16 wk, ≥ 4 in 8 wk)	
Major response: Major HI-E response in HTB patients corresponds to transfusion independence, defined by the absence of any transfusions over a period of minimum 8 wk in an observation period of 16-24 wk with the same transfusion policy (defined below) compared with 16 wk prior to treatment; only a response duration of at least 16 wk, however, is considered clinically meaningful
 
Minor response: Minor HI-E response in HTB patients is defined as a reduction by at least 50% of RBCs over a minimum of 16 wk with the same transfusion policy (defined below) compared with 16 wk prior to treatment

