Platelet response (HI-P) (pretreatment, $< 100 \times 10^9/L$)	
 Absolute increase of $30 \times 10^9/L$ for patients starting with $>20 \times 10^9/L$ PLTs or Increase from $<20 \times 10^9/L$ to $>20 \times 10^9/L$ and by at least 100% 
In addition,
 
 Evolution of bleeding symptoms is to be taken into account Increments of platelets also for patients with a pretreatment PLT count of $>100 \times 10^9/L$ are to be reported
Neutrophil response (HI-N) (pretreatment, all patients)	
 At least 100% increase and an absolute increase $>0.5 \times 10^9/L$ (pretreatment, $<1.0 \times 10^9/L$) Increments of neutrophils also for patients with a pretreatment ANC of $>1.0 \times 10^9/L$ are to be reported
Progression or relapse after HI†	
At least 1 of the following:
 
 At least 50% decrement from maximum response levels in granulocytes or platelets Reduction in Hb by ≥ 1.5 g/dL Transfusion dependence

†Certain targeted therapies, for example, those inhibiting mutant IDH proteins, may cause a differentiation syndrome, that is, a transient increase in the percentage of bone marrow blasts and an absolute increase in blood blasts; in the setting of therapy with such compounds, an increase in blasts may not necessarily indicate PD.

b) IWG 2023 response criteria for HR-MDS

For secondary endpoint and MDS population only

RESPONSE	DEFINITION
Complete remission (CR)	
 BM: $<5\%$ myeloblasts*; dysplasia may persist PB: Hb ≥ 10 g/dL, platelets $\geq 100 \times 10^9/L$; neutrophils $\geq 1.0 \times 10^9/L$; blasts $0\%^\dagger$
CR equivalent*	
Patients with $<5\%$ BM blasts at baseline:
 
 BM: $<5\%$ myeloblasts*; dysplasia may persist PB: Hb ≥ 10 g/dL, platelets $\geq 100 \times 10^9/L$; neutrophils $\geq 1.0 \times 10^9/L$; blasts $0\%^\dagger$ Full cytogenetic clearance of baseline abnormalities (complete cytogenetic response)
Partial remission (PR)	
All CR criteria except:
 
 BM blasts decreased by $\geq 50\%$ over pretreatment but still $\geq 5\%$ Cellularity and morphology not relevant

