CR _L § (CR _{uni} and CR _{bi})	
 BM: $<5\%$ myeloblasts*; dysplasia may persist PB: blasts $0\%^\dagger$ CR_{uni}: PB, not meeting CR but only 1 of the following: Hb ≥ 10 g/dL; platelets $\geq 100 \times 10^9/L$; neutrophils $\geq 1.0 \times 10^9/L$ CR_{bi}: PB, not meeting CR but only 2 of the following: Hb ≥ 10 g/dL; platelets $\geq 100 \times 10^9/L$; neutrophils $\geq 1.0 \times 10^9/L$
CR _h §	
 BM: $<5\%$ myeloblasts*; dysplasia may persist PB: Not meeting criteria for CR or CR_L, no Hb threshold required, platelets $\geq 50 \times 10^9/L$; neutrophils $\geq 0.5 \times 10^9/L$; blasts $0\%^\dagger$
HI	
HI defined according to IWG 2018 response criteria:II
 
 Not meeting criteria for CR (or CR equivalent) or CR_{uni} or CR_L HI_{erythroid} (HI-E) HI_{platelets} (HI-P) HI_{neutrophils} (HI-N)
ORR	ORR = CR (or CR equivalent)* + PR + CR _L + CR _h + HI
No response	Not meeting criteria for CR (or CR equivalent)*, PR, CR _L , CR _h , or HI†
Not evaluable	All registered/randomly assigned patients should be reported in the denominator of response assessment analyses in line with the intention-to-treat principle. This category may include patients yet to have a response assessment, suffering early

	death, exiting the study early, or those with a technically suboptimal BM sample precluding assessment.
Cytogenetic response¶	
 Complete: disappearance of the chromosomal abnormality without appearance of new ones. Partial: ≥50% reduction of the chromosomal abnormality.
Progressive disease (PD)	
Fulfilling any of the criteria below: #, **, ††
 
 Disease progression by blasts: ≥50% relative increase in blasts and absolute increase of blast percentage by at least 5% from pretreatment sample taken before current line of therapy Disease progression by worsening cytopenia: new, repeated (more than once and separated by ≥7 days) need for RBC or platelet transfusions within 8 weeks, not related to acute intercurrent illness (eg, sepsis, gastrointestinal tract bleed) or treatment effect, in the absence of HI of at least one other blood lineage as defined above Progression to AML: ≥50% increase in blasts from baseline assessment to ≥20% blasts.

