#### 7.7.6 Progression-free-survival

Progression-free-survival (PFS) will be defined as the duration of time from time of treatment to time of progression or death, whichever occurs first. A subject who has neither progressed (defined as first time having Progressive disease (PD) or Progression or relapse after HI on response assessment) nor died will be censored on the date of the last observation. Therefore:

In case there was a progression or death:

PFS [days] = min(date of progression/death) – Drug administration date in Visit [REDACTED] +1

Otherwise, censoring date will be:

PFS [days] = date of last observation – Drug administration date in Visit [REDACTED] +1

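### PFS has no AML-transformation event, so an MDS patient can reach AML-range blasts and still be stable disease; the progression-after-HI row also needs tightening

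*Protocol*

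**What the plan says.** SAP 7.7.6 runs PFS to progression or death, with progression "defined as first time having Progressive disease (PD) or Progression or relapse after HI on response assessment". Both categories come from the combined AML/MDS table in Protocol 16.3 Appendix III a), repeated in SAP Appendix 2 a).

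- **Progressive disease (PD).** In marrow, blasts must rise by more than 50%. For baselines under 30% there is an added condition: "a minimum 15%-point increase is required in cases with" such a baseline. Outside the marrow, PD needs a rise of more than 50% in blood blasts to above 25 x 10^9/L, or new extramedullary disease. Stable disease (SD) is what remains when neither a remission category nor PD applies.
- **Progression or relapse after HI.** Any one of three findings is enough: "At least 50% decrement from maximum response levels in granulocytes or platelets", a hemoglobin fall of at least 1.5 g/dL, or "Transfusion dependence". The dagger on this row leads to a note about differentiation syndrome, which does not limit any of the three.

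Appendix III b) (IWG 2023) has its own AML event: a rise of at least 50% in blasts, to 20% or more. It serves only the MDS response endpoint at visit 9 (SAP 7.7.9). Protocol 9.3.2 exempts events due purely to disease progression from expedited reporting, "except transformation to AML which is always to be reported as an SAE".

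**The concern.** Protocol 1.1.1 uses 20% blasts as the boundary between MDS and AML, and the safety section treats crossing it as always reportable. PFS can pass over the same event and go on accruing progression-free time. PFS is a named secondary endpoint and is reported by cohort, so a missed transformation lengthens PFS in MDS patients.

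The HI row raises the opposite problem on a smaller scale. An HI-N responder whose platelets halve meets it, although the neutrophil response may be intact. Transfusion dependence is undefined and need not be new, so a patient with HI in platelets or neutrophils and an unchanged red-cell need can be read as progressed. So can a minor HI-E responder, who by definition may still be transfused.

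**Working it through.** The plan states no PFS figure to reproduce, so the check applies the two progression rules to the same patients.

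**Inputs.** Entry needs at least 5% marrow blasts (Protocol 6.3, criterion 8). MDS runs to 19% (Appendix I). AML starts at 20% (Protocol 1.1.1). Let b be baseline blasts in percent.

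**Thresholds.**
- Appendix III a) marrow PD: a rise above 0.5b and of at least 15 points. For b from 5 to 19, 0.5b is at most 9.5, so the 15-point condition decides and the threshold is b + 15.
- Appendix III b) progression to AML: max(20, 1.5b).
- Gap = (b + 15) - max(20, 1.5b).

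| b (%) | a) PD from | b) AML from | Gap (points) | Whole-number blasts that are AML progression in b) but not marrow PD in a) |
|---|---|---|---|---|
| 5 | 20 | 20 | 0 | none |
| 6 | 21 | 20 | 1 | 20 |
| 10 | 25 | 20 | 5 | 20-24 |
| 12 | 27 | 20 | 7 | 20-26 |
| 13 | 28 | 20 | 8 | 20-27 |
| 14 | 29 | 21 | 8 | 21-28 |
| 15 | 30 | 22.5 | 7.5 | 23-29 |
| 19 | 34 | 28.5 | 5.5 | 29-33 |

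**Worked cases.** From 12% to 26% is +14 points and 26/12 = 2.17 times baseline. From 10% to 22% is +12 points and 2.2 times baseline. Both are SD under a) and progression to AML under b), unless the blood-blast or extramedullary route applies.

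**Residual gap.** At baselines of 14% to 19%, blasts can pass 20% without a 50% relative rise (for example 15% to 20-22%). The listed AML rule in b) does not count these either; one of its footnotes leaves them to clinical context.

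**HI row.**
- Minor HI-E: 8 red-cell units in 16 weeks falling to 4 is a 50% reduction and so a response. Four units still lies in the appendix's own 3-7 unit low-burden class, so the patient is still being transfused when response is scored.
- Relapse by counts in Appendix III b) also uses a halving or a 1.5 g/dL hemoglobin fall, but adds floors in the same line: Hb <10 g/dL, platelets <100 x 10^9/L, neutrophils <1.0 x 10^9/L. A platelet maximum of 200 (2 x 100), a neutrophil maximum of 2.0 (2 x 1.0) or an Hb maximum of 11.5 (10 + 1.5) can meet the a) criterion without breaching the floor.

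**The case against.** The best defence is that one criterion for AML and MDS was a deliberate choice (Protocol 5.1.3), all analyses are exploratory (Protocol 10.1), and the investigator records the category. The row is also headed as progression or relapse *after* HI and refers to a maximum response level. Both suggest a loss in a line that had responded, so unchanged transfusion need is arguably neither. This stands in part: the HI problem is an ambiguity to close, not a proven miscount. None of it supplies an AML event.

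A reader might go further and infer that imetelstat's own cytopenias will be scored as progression, so that PFS no longer measures disease control. The protocol does say "Cytopenias, particularly thrombocytopenia and neutropenia, are the primary dose limiting toxicities (DLTs) identified with imetelstat", and the HI row has no exclusion by cause. The documents still do not support that inference:

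- The same section says "cytopenias are manageable through dose modifications, reversible and of short duration". Procedures precede dosing (Protocol 8.1.4), and dosing visits wait until the patient can be dosed (8.1.7). SAP 7.7.6 counts what is recorded at a response assessment, so a nadir between visits is not an event.
- Appendix III b) is no precedent for excluding count falls by cause. Its phrase "not related to acute intercurrent illness (eg, sepsis, gastrointestinal tract bleed) or treatment effect" qualifies transfusion need. For count falls it uses floors.
- Only patients who first had HI are exposed. The SAP document history reports no responders at the interim analysis, and the planning response rate was 20% (Protocol 10.3). The median and landmark PFS cannot be called invalid on this ground.
- No document gives the within-patient variability of counts, so a rate of chance halving cannot be derived.

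**Conclusion.** The AML half holds on the current text. For every whole-number MDS baseline from 6% to 19% there is a range of marrow blasts that Appendix III b) calls progression to AML and the PFS rule leaves as SD. The gap is 0 at 5%, peaks at 8 points at 13-14%, and is 5.5 points at 19%. This assumes that the criteria are applied as written and that neither the blood-blast nor the extramedullary route is met. How many patients fall in the gap cannot be known from the documents.

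The HI half holds in a narrower form: the row is not tied to the improved line, and transfusion dependence need not be new. It can affect PFS only in HI responders, so with none at the interim it is the less material part. It would be too strong to say that any count fall in any patient ends PFS, or that PFS is driven by toxicity. Because the analysis is exploratory, this is a worthwhile improvement to the SAP rather than a threat to the trial's conclusions.

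**What to change.** 1. Keep the harmonized PFS. Add to Table 14.6.2 an MDS-only PFS line, by cohort, with PD under SAP Appendix 2 b), including progression to AML, as the event. Derive it at each response assessment from the marrow blasts, counts and transfusions already collected.
2. In SAP 7.7.6, count progression or relapse after HI only in a line in which HI was scored. Count transfusion dependence only when it is new, that is, after transfusion independence in that line.
3. As a sensitivity analysis, apply the count floors of Appendix 2 b) disease relapse: Hb <10 g/dL, platelets <100 x 10^9/L, neutrophils <1.0 x 10^9/L.

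Do not add attribution of count falls to treatment; in an open-label trial after an interim look, that would be a judgement made with the data in view.

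**Cost.** SAP text and programming only; SAP 2.10 allows updates before database lock. PFS in MDS will appear under two criteria. The new line will also pick up earlier events, because Appendix 2 b) counts blast progression from max(b + 5, 1.5b), for example 18% at a 12% baseline. Its transfusion limb needs a judgement of cause, for which the reason for transfusion is recorded (Protocol 8.2.4.2). Its time windows are in a publication table that neither document reproduces, so the SAP must write them out. Part 3 of the schedule has no local marrow cytology after treatment ends, so patients no longer counted as events may be censored early; report how many.

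This concerns PFS event counting only. Where the same criteria govern treatment (Protocol 5.1.4 and 7.7), the sponsor must reconcile the passages.

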16.4 Appendix IV: Eastern Cooperative Oncology Group (ECOG) Performance Status Scale

Grade	ECOG
0	Fully active, able to carry on all pre-disease performance without restriction.
1	Restricted in physically strenuous activity but ambulatory and able to carry out work of a light or sedentary nature (e. g. light house work, office work).
2	Ambulatory and capable of all self-care but unable to carry out any work activities. Up and about more than 50 % of waking hours.
3	Capable of only limited self-care, confined to bed or chair more than 50 % of waking hours.
4	Completely disabled. Cannot carry on any self-care. Totally confined to bed or chair.
5	Dead.

Source: Oken MM, Creech RH, Tormey DC, Horton J, Davis TE, McFadden ET, et al. Toxicity and response criteria of the Eastern Cooperative Oncology Group. Am J Clin Oncol 1982;5(6):649-55.

16.5 Appendix V: Sample of QoL questionnaire

A PDF file of the EORTC QLQ-C30 can be downloaded without charge at:

<https://www.eortc.org/app/uploads/sites/2/2018/08/Specimen-QLQ-C30-English.pdf>

(Access date: March 18th, 2022)

16.6 Appendix VI: CTCAE Version 5.0

Toxicity will be scored using CTCAE Version 5.0 for toxicity and adverse event reporting.

A PDF file of CTCAE v 5.0 can be downloaded without charge at

https://ctep.cancer.gov/protocoldevelopment/electronic_applications/docs/CTCAE_v5_Quick_Reference_5x7.pdf

Published: November 27th, 2017

16.7 Appendix VII: List of prohibited concomitant medications

The following medications are prohibited during the study:

- ESAs therapy
- Chemotherapy
- Hypomethylating agents
- Immunotherapy
- Any experimental therapy / study drug other than imetelstat
- Corticosteroids
 - Systemic use of corticosteroids in excess of prednisone 20 mg/day or its equivalent for more than 10 days is prohibited unless reviewed and approved by the sponsor's medical monitor.
 - Long-term, chronic use of corticosteroids at any dose should also be reviewed and approved by the sponsor's medical monitor.
 - Corticosteroids used as premedication are permitted.

The following medications can be applied after prior discussion with the sponsor:

- Radiotherapy
- Immunomodulatory agents (eg, lenalidomide),

The following concomitant anti-leukemic medication is allowed:

- Hydroxyurea is allowed
- Radiotherapy is allowed at the discretion of the sponsor
- All other anti-leukemic treatments are prohibited

The sponsor must be notified in advance (or as soon as possible thereafter) of any instances in which prohibited therapies are administered.

## Document History

Version	Date	Author(s)	Description
v0.1	21-SEP-2023	██████████	First draft
v1.0	23-FEB-2024	██████████	Finalization
v1.1	03-SEP-2024	██████████	Substantial modification after interim analysis based on interim analysis data showing no responders according to response assessment criteria.
V2.0	19-DEC-2024	██████████	Finalization
V2.1	09-OCT-2025	██████████	
 
• Trial schedule update after Protocol amendment v6.0 (see 2.4)
 
• Rename of section 7.7.3 and addition of censoring in section 7.7.13
 
• Update of references errors
 
• Inclusion of baseline characteristics tables and listings (see 8.2.2)
 
• Inclusion of Serum chemistry and Vital Signs tables (see 8.5.4) for the analysis aligning with protocol section 10.9.4
 

			
 
• Inclusion of Dose Modifications listing (see 8.5.3) aligning with protocol section 10.9.2)
 
• Restructuring of sections 6.1, 6.2.3, 8.5.3, 8.5.4, 8.6 and 8.7 for a better structure of the additional endpoints. Extent of exposure and laboratory other endpoints moved to safety endpoint to be analysed in SES aligning with protocol sections 10.9.2 and 10.9.4.
 

V3.0	13-OCT-2025		
 
• Finalization
 

## List of Abbreviations and Key Terms

Abbreviation	Definition
$\alpha$	Type I error
$\beta$	Type II error
AE	Adverse Event
ALT	Alanine aminotransferase
AML	Acute myeloid leukemia
ANC	Absolute Neutrophil Count
ATC	Anatomical Therapeutic Chemical
AUS	Australia
BID	Twice per day
BM	Bone marrow
BMI	Body Mass Index
BSC	Best supportive care
CBC	Complete blood count
CFB	Change from baseline
CI	Confidence Interval
CPI	Coordinating Principal Investigator ( Leiter der klinischen Prüfung )
CR	Complete Remission
CRi	Complete Remission with Incomplete recovery
CRO	Contract Research Organization
CSR	Clinical study report
CTCAE	Common Terminology Criteria for Adverse Events
DRM	Data Review Meeting
ECG	Electrocardiogram
ECOG PS	Eastern Cooperative Oncology Group Performance Status

eCRF	Electronic case report form
EOS	End of Study
EOT	End of Treatment
FAS	Full analysis set
FU	Follow-up
GCP	Good clinical practice
Hb	Hemoglobin
HI	Hematologic Improvement
HI-E	Hematological improvement - erythroid
HI-N	Hematological improvement - neutrophils
HI-P	Hematological improvement - platelets
HMA	Hypomethylating agents
HRQoL	Health-Related Quality of Life
IA	Interim Analysis
ICF	Informed consent form
IEC	Independent ethics committee
IMP	Investigational Medicinal Product
IWG	International Working Group
LDH	Lactate Dehydrogenase
LPEOS	Last patient end of study
MCH	Mean corpuscular hemoglobin
MCHC	Mean corpuscular hemoglobin concentration
MCV	Mean corpuscular volume
MDS	Myelodysplastic syndrome
MedDRA	Medical Dictionary for Regulatory Activities
MLFS	Morphologic Leukemia-Free State
Min	Minimum

Max	Maximum
Miss	Missing observations
NCI	National Cancer Institute
nRBC	nucleated Red Blood Cells
OS	Overall survival
ORR	Overall Response Rate
PB	Peripheral blood
PD	Progressive Disease
pEP	primary Endpoint
PFS	Progression-Free Survival
PPS	Per Protocol Set
PR	Partial Remission
pRBCs	Packed red blood cells
PRN	As needed
PT	Preferred Term
Q2W	Every two weeks
Q1	Lower quartile
Q3	Upper quartile
QD	Per day
QID	4 times per day
QIMRB	Queensland Institute of Medical Research Berghofer
QOD	Every other day
QoL	Quality of life
QM	Per month
RBC	Red blood cell
RDW	Red blood cell distribution width
RS	Raw Score

S	Final Score
SAE	Serious adverse event
SAP	Statistical Analysis Plan
SD	Stable Disease
SDTM	Study Data Tabulation Model
SDev	Standard Deviation
SES	Safety Evaluation Set
SGOT	Serum glutamic oxaloacetic transaminase
SGPT	Serum glutamic pyruvic transaminase
SOC	System Organ Class
SUSAR	Suspected unexpected serious adverse reaction
TEAEs	Treatment emergent adverse events
TID	3 times per day
ULN	Upper limit of normal
UMVUE	Uniformly minimum variance unbiased estimator
WBC	White blood cell count
WHO	World Health Organization

